4.4 Consent Procedures

A. Consent Process

- **Location of Consent Process**
Consent will take place in person at University Orthopaedics Associates, LLC outpatient surgery center located at [name].
- **Ongoing Consent**
Patients are free to remove themselves from the study at any time. Unenrolling from the study will not affect their care in any way.
- **Individual Roles for Researchers Involved in Consent**
Physicians listed in study staff will be primarily involved in identification of patients and consent. Study staff including anesthesiologist, resident, and support staff listed will also be able to discuss study with patients. Potential study participants will be led through the consent process by research coordinator or study investigators, using an IRB-approved consent form.
- **Consent Discussion Duration**
The consent discussion will be given as much time as is needed for the potential subject to make an informed decision. We estimate that each patient will require around 20 minutes to complete the consent process, but patients are free to extend the duration as needed.
- **Coercion or Undue Influence**
In order to minimize the potential for coercion or undue influence, all participants will be given ample time to ask questions and to make an informed decision about study participation. A member of the study team will ensure that the potential participant fully understands the details of the study and comprehends the significance of his/her decision to consent for participation. Participating in this study will determine how they receive their instructions for surgery. Lastly, all potential participants will be assured that their current or future care will not be affected by their decision to participate.
- **Subject Understanding**
The “teach-back method” will be implemented. The study team member leading the consent discussion will ensure the subject’s understanding of the study by asking them to paraphrase the information conveyed in the consent form. Potential subjects will also be encouraged to ask questions throughout the consent process to clarify any points of confusion that arise.
- **Protecting Privacy**
Consent will take place privately in the private examination room at the UOA office.

B. Waiver or Alteration of Consent Process

- **Waiver or Alteration Details**
N/A
- **Destruction of Identifiers**
N/A
- **Use of Deception/Concealment**
N/A
 - a. **Minimal Risk Justification**
N/A
 - b. **Alternatives**
N/A
 - c. **Subject Debriefing**
N/A

C. Documentation of Consent

- **Documenting Consent**
Potential subjects will have an informative conversation with the surgeon and research coordinator/ancillary staff at their preoperative visit to assess their interest in participating in

the study. The subject will be given the opportunity to read the study informed consent and to ask any questions. If the subject agrees to participate and signs the informed consent, the subject will be given a copy of the informed consent.

- **Waiver of Documentation of Consent (i.e., will not obtain subject's signature)**
N/A

4.5 Special Consent Populations

A. Enrolling Minors-Subjects Who Are Not Yet Adults

- **Parental Permission**
All participants will be above the age of 18 and will provide informed consent for themselves.
- **Non-Parental Permission**
N/A
- **Assent Process**
N/A
- **Documentation of Assent**
N/A
- **Reaching Age of Majority During Study**
N/A

B. Enrolling Wards of the State

- **Research Outside of NJ Involving Minors**
N/A

C. Enrolling Non-English-Speaking Subjects

- Non-English speaking patients will be excluded from the study.
- **Process for Non-English-Speaking Subjects**
N/A
 - **Short Form Consent for Non-English Speakers**
N/A

D. Enrolling Adults Lacking Decision-Making Capacity (Surrogate Consent)

- Patients who lack decision-making capacity will be excluded from the study.
- **Assessing Adult Capacity to Consent**
N/A
 - **Selecting a Surrogate & Consent Process**
N/A
 - **Subject Assent**
N/A
 - **Selecting a Witness to the Surrogate Consent Process**
N/A
 - **Removing a Subject**
N/A

E. Special Consent Considerations

N/A

4.6 Economic Burden and/or Compensation for Subjects

A. Expenses

There will be no additional costs to the patient. Each patient who enrolls will need to have a cell phone that can be used to receive messages and view the instructional video. These messages and videos will not cost the patient any money. Any patient that does not have access to a cell phone will be excluded from the study.

B. Compensation/Incentives

There is no compensation for participation in this study.

C. Compensation Documentation

N/A

4.7 Risks of Harm/Potential for Benefits to Subjects

A. Description of Risks of Harm to Subjects

- **Reasonably Foreseeable Risks of Harm**
There are no risks associated with participation in this study.
- **Risk of Harm from an Intervention on a Subject with an Existing Condition**
N/A
- **Other Foreseeable Risks of Harm**
N/A
- **Observation and Sensitive Information**
N/A

B. Procedures which Risk Harm to Embryo, Fetus, and/or Pregnant Subjects

N/A

C. Risks of Harm to Non-Subjects

N/A

D. Assessment of Social Behavior Considerations

N/A

E. Minimizing Risks of Harm

N/A.

- **Certificate of Confidentiality**

N/A

- **Provisions to Protect the Privacy Interests of Subjects**

Patient confidentiality will be maintained by storing collected data on a password protected document and stored on the Rutgers approved Office cloud - OneDrive. Only the research team will have access to this information. Any publication that may come of this research study will not reveal any identifying information about the subjects.

F. Potential Direct Benefits to Subjects

The goal of this research is to provide patients with an ideal/ effective method of perioperative education that will improve patient comprehension of operative instructions. Effective patient education on care for surgical incision, how to safely manage pain with and without opioids, the side effects of opioids, may minimize risks associated with opioids including adverse effects and the risk of developing an opioid dependence in the post-operative setting.

5.0 Special Considerations

Complete each sub-section that applies to the research; if not applicable, replace instructional text with N/A.

5.1 Health Insurance Portability and Accountability Act (HIPAA)

All patients will be provided with a standard HIPAA practices agreement at the office visit.

5.2 Family Educational Rights and Privacy Act (FERPA)

N/A

5.3 Code of Federal Regulations Title 45 Part 46 (Vulnerable Populations)

N/A

A. Special Populations

- N/A

5.4 General Data Protection Regulation (GDPR)

N/A

5.5 NJ Access to Medical Research Act (Surrogate Consent)

N/A

6.0 Data Management Plan

6.1 Data Analysis

Data will be analyzed by the statisticians. Statistical comparisons will be made between patients receiving paper instructions vs. video instructions. The mean number of questions answered correctly for both the groups were compared using the student t-test. For secondary variables and baseline characteristics, statistical testing was performed based on the type of variable: the chi-square test for categorical variables and the student t-test (parametric) or Mann-Whitney U test (nonparametric) for continuous variables. For the ordinal variable of patient-reported helpfulness, the Mann-Whitney U test was used.

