1.3 Research Design and Methods

This is a single-blinded prospective randomized controlled clinical trial. Patients 18 or older, undergoing a meniscectomy procedure at University Center for Ambulatory Surgery, LLC (UOA), who are English speaking, with intact decision-making capacity, and have access to the required technology to participate in this study (cell phone to receive text messages and view the instructional video), will be reviewed for eligibility. Patients who did not speak English and/or had documented cognitive impairment or neurological disorder affecting word processing or memory will be excluded from the study. Once identified, potential study subjects will be asked whether they are interested in participating in the project. If the patient agrees, the subject will be given the informed consent to read and sign.

A. Research Procedures

Preoperative Visit: All patients who consent will have operative instructions explained by the study surgeon and his assistants. Patients will then be allocated to either the video or handout group with the use of a computer-generated block randomization sequence, with the study surgeon blinded to patient allocation. Due to the nature of the material provided, it is not possible to blind the patients to the allocation. Patients in the control group will be given a physical copy of the handout of operative guidelines at the time they book their surgery in the office. Those in the study group will receive a link at the same time point when they book their surgery in the office, via email, which will provide access to a video on YouTube outlining the same operative instructions. A research assistant will confirm patients in the study group receive the video by email and that the link was playable/ accessible to them.

Patients in both groups will be aware that they would be asked questions regarding the contents of the instructions. Patients had unlimited access to the video once they were provided the link. The

video was less than 10 minutes long, and it was accessible by computer, tablet, or cell phone. The content of the video and paper handout mirrored each other and consisted of general operative instructions, incision and dressing care, symptom monitoring, and pain management (Video 1, Appendix 1).

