Day of Surgery: All patients will be receiving the same preoperative care, undergo meniscectomy via the same surgical technique, and same postoperative care in the post-anesthesia care unit (PACU) after surgery. In the PACU, patients in the control group will again be given a physical copy of the handout of operative guidelines. Likewise, patients in the study group will also be sent a link by email, again in the PACU after surgery.

After surgery: At the first postoperative visit, 10 to 14 days after surgery, patients will be given a questionnaire to evaluate their comprehension of concepts which were outlined in the video or the handout. The questionnaire will consist of 12 multiple choice questions with concepts including areas such as how to care for the incision, how to safely manage pain with and without opioids, the side effects of opioids (Questionnaire in supplemental section of eIRB). Patients will also be asked to rate how helpful they found the information in the assigned instructions on a scale of 1 to 5 (1 = not at all helpful, 5 = extremely helpful), how many times they viewed the instructions, and at what time point the instructions were most helpful to read (before the procedure, at the surgical center, or after the procedure). Lastly, patients will be asked to report the number of opioid and other analgesic medications they took following surgery.

B. Data Points

Age, injury type, surgery performed, use of narcotic and other analgesic pain medication, number of times instructions viewed or read

C. Study Duration

The study will be conducted from time of IRB approval until the minimum number of participants shown below have completed the study. Each subject will participate in the study from their pre-operative appointment until 14 days after surgery.

D. Endpoints

Primary endpoints: The number of questions answered correctly, and patient-reported helpfulness of the material, on a scale of 1-5 to detect clinically significant difference in patient comprehension.

Secondary endpoint: Number of opioid and other analgesic medications taken

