1.5 Sample Size Justification

PG Power Table			Primary 2 Arm Treatment Comparison		Primary 2 Arm Treatment + Anesthesia Subgroup Comparison	
Statistical Significance	Power	Desired Effect Size	N per Treatment Type (2 Groups) 0% Drop-Out Inflation	N per Treatment Type (2 Groups) 20% Drop-Out Inflation	N per Treatment Type (4 Groups) 0% Drop-Out Inflation	N per Treatment Type (4 Groups) 20% Drop-Out Inflation
0.05	0.80	0.50 (medium)	64	80	128	160
0.05	0.80	0.60 (medium)	45	57	90	114
0.05	0.80	0.70 (medium)	34	43	68	86
0.05	0.80	0.80 (large)	26	33	52	66

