4.0 Subject Considerations

4.1 Subject Selection and Enrollment Considerations

A. Method to Identify Potential Subjects

Patients 18 or older, undergoing a meniscectomy procedure at University Center for Ambulatory Surgery, LLC (UOA) will be reviewed for eligibility.

B. Recruitment Details

Recruitment will take place at the UOA office during patient visits. Patients will be provided with educational pamphlet. Recruitment will take place by study staff.

C. Subject Screening

Subjects will be screened by attending physicians in the office setting as patients are being indicated for surgery as per standard of care.

▪ Inclusion Criteria

- Patients 18 or older
- Undergoing a meniscectomy procedure
- English speaking
- Intact decision-making capacity
- Have access to the required technology to participate in this study (cell phone to receive text messages and view the instructional video)

▪ Exclusion Criteria

- Patients who did not speak English
- Patients with documented cognitive impairment or neurological disorder affecting word processing or memory
- Patients who do not have access to a cell phone to view the video

D. Privacy Protections

Data collected via an online questionnaire that is protected by HIPPA regulations. Data will be de-identified prior to statistical analysis.

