4.3 Number of Subjects

A. Total Number of Subjects

80-160 patients targeted to be recruited to account for study dropout

B. Total Number of Subjects If Multicenter Study

N/a

C. Feasibility

University Orthopaedic Associates is a high-volume orthopaedic center. Physicians including Drs. [name], [name], [name], and [name] see a high volume of patients undergoing meniscectomy and it is therefore reasonable to accrue the required number of patients to achieve statistical significance for this study.

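### The comprehension score is analysed without covariates and baseline data are significance-tested, while the listed data points hold no measure of education or prior knowledge; recording and adjusting for education would be a cheap gain in precision.

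*Protocol*

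**What the plan says.** Section 6.1 fixes the primary comparison as a two-sample test with no covariates: "The mean number of questions answered correctly for both the groups were compared using the student t-test". For other variables it says: "For secondary variables and baseline characteristics, statistical testing was performed based on the type of variable", with the test chosen as chi-square, Student t or Mann-Whitney.

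The data points in section 1.3 B are "Age, injury type, surgery performed, use of narcotic and other analgesic pain medication, number of times instructions viewed or read". Of these, age, injury type and surgery performed describe the patient; the rest are outcome or exposure data. Education, health literacy and a score taken before the instructions are not listed.

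Allocation uses a "computer-generated block randomization sequence" (section 1.3 A), with no stratification factor named. The comprehension questionnaire has 12 items and is given once, at the first postoperative visit. Section 4.1 excludes "Patients with documented cognitive impairment or neurological disorder affecting word processing or memory", and non-English speakers are also excluded.

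**The concern.** Two separate things are at issue.

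- **Baseline tests.** When allocation is random, the null hypothesis of a baseline test is true by design. The p-value does not say whether a chance difference is large enough to matter for the outcome, and in a trial of this size a sizeable difference can pass as non-significant.
- **The primary model and its data.** A single post-treatment knowledge score carries all the spread between patients in schooling, literacy and prior knowledge, and an unadjusted t-test leaves that spread in the error term. A later analysis plan could add a covariate to the model, but it cannot supply a variable that was not collected before allocation.

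At stake is power for the primary endpoint, and how easily a reader can interpret the result if the arms happen to differ in education.

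**Working it through.** **Inputs from the protocol.** Section 1.5: alpha 0.05 (taken as two-sided), power 0.80, effect 0.50 SD, 64 per arm, 80 per arm with "20% Drop-Out Inflation". Section 4.3: "80-160 patients targeted to be recruited to account for study dropout". Equal allocation is assumed from the equal arm sizes.

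**Inputs assumed.** The correlation ρ between education and score is taken as 0.2 to 0.5, and half the patients are taken to have higher education. Neither figure is in the protocol.

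**Step 1. Reproduce the plan's figure.** A two-sample t-test (noncentral t) at an effect of 0.50 gives 64 per arm, with power 80.1%. Drop-out: 64 / (1 − 0.20) = 80. The other two-arm rows also match: 45, 34 and 26 per arm, inflated to 57, 43 and 33. No stated number is wrong.

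**Step 2. What adjustment is worth.** Adjusting for one baseline covariate multiplies the residual variance by 1 − ρ². The effect in residual SD units becomes 0.50 / √(1 − ρ²), and the sample size needed becomes 64 × (1 − ρ²), rounded up.

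| ρ (assumed) | 1 − ρ² | N per arm for 80% power | Saved per arm | Power at 64 per arm |
|---|---|---|---|---|
| 0 | 1.00 | 64 | 0 | 80.1% |
| 0.2 | 0.96 | 62 | 2 | 81.7% |
| 0.3 | 0.91 | 59 | 5 | 83.7% |
| 0.4 | 0.84 | 54 | 10 | 86.5% |
| 0.5 | 0.75 | 48 | 16 | 90.0% |

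Taking two degrees of freedom off the error term (126 to 124) changes these powers by less than 0.1 percentage point. If only 80 are enrolled and 20% drop out, 80 × 0.8 / 2 = 32 per arm remain; power at 0.50 SD then goes from 50.4% to 52.0% (ρ = 0.2) or 62.3% (ρ = 0.5). Any further gain from age is not counted.

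**Step 3. How large a chance difference in education could be.** With half the patients in the higher category, the standard error of the difference in shares is √(2 × 0.25 / n).

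- At 64 per arm it is 0.088. A gap of 10 points or more occurs in about 26% of trials, and 15 points or more in about 9%.
- At 32 per arm it is 0.125. A gap of 10 points or more occurs in about 42% of trials.

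A 15-point gap is 0.15 / 0.5 = 0.30 SD of the covariate. It moves the score difference by 0.30 × ρ, which is 0.06 SD at ρ = 0.2 and 0.15 SD at ρ = 0.5.

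**Step 4. What a baseline test would show.** The smallest observed difference in a continuous variable that reaches p < 0.05 is the critical t times √(2/n).

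- 64 per arm: 1.979 × 0.177 = 0.35 SD.
- 40 per arm: 1.991 × 0.224 = 0.445 SD.
- 32 per arm: 1.999 × 0.25 = 0.50 SD.

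An observed imbalance of 0.30 SD would be reported as non-significant at each of these sizes.

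**The case against.** The strongest reply is that nothing here invalidates the primary comparison. Under randomization the t-test's standard error already allows for chance imbalance, so there is no bias and no inflation of the type I error. That stands. A reader might infer that, without education, the trial could not tell a video effect from the effect of a better educated arm; the design does not support that reading.

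Other parts of the reply also stand:

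- Section 6.1 does not say that the baseline tests decide comparability, select covariates or alter the primary analysis. Dropping the p-values would by itself change no result.
- A reader might infer that education is never recorded. The list in 1.3 B is visibly incomplete: it omits the comprehension score and the helpfulness rating, both of which are collected. The questionnaire sits in a supplement that is not shown. Only absence from the listed data points is established.
- A reader might infer that surgery performed is being treated as a baseline variable. The protocol does not call it one and never defines its baseline set.
- Age is recorded and may relate to recall, so the listed variables are not all irrelevant to the score. The exclusion for cognitive impairment does not show that the protocol regards schooling as a driver of it.
- The correlation is assumed. At 0.2 to 0.3 the saving is only 2 to 5 patients per arm. The shift from a 15-point education gap (0.06 to 0.15 SD) is well below the smallest planned effect of 0.50 SD.

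It can also be said that covariate adjustment and the format of the baseline table belong in a statistical analysis plan. That is fair for the model and the table. It does not cover data collection, which has to be settled before patients are allocated.

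**Conclusion.** The point holds as a minor, inexpensive improvement and not as an error in the primary analysis. Section 6.1 plans baseline tests that carry no information after randomization, and it fixes an unadjusted analysis of a knowledge score for which no measure of education, literacy or prior knowledge is among the listed data points. The cost is precision: power of 80% where about 82-90% could be had at 64 per arm and an effect of 0.50 SD. That range rests wholly on an assumed correlation of 0.2 to 0.5 and on education not already being captured on a form that is not shown. The stated sample sizes are correct and need no change.

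**What to change.** - **Section 1.3 B:** add highest education completed, asked at consent before allocation. If the data-entry forms already hold it, list it.
- **Section 6.1, primary analysis:** replace the unadjusted t-test with a linear model for the number of correct answers, with arm, education and age as prespecified terms. Report the adjusted difference between arms with its 95% confidence interval. The unadjusted difference can be shown alongside.
- **Section 6.1, baseline data:** describe them by arm (mean and SD, or number and percentage) without p-values.

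The cost is one extra question per patient, a minor amendment, and about one degree of freedom per covariate term. Patients already enrolled will have missing values unless they are asked later. Arms, sample size and clinical care are unaffected.

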6.2 Data Security

Describe the steps that will be taken to secure the data through all phases of the research—from the time of its collection, to its storage, use and study closure— such as staff training, transporting or transmitting data from the study site or ‘field’ to Rutgers, methods to restrict access, password protection, encryption, use of key codes to separate identifiers from the data, and state how and when identifiers will be deleted from the data. Identify who will be responsible for each of these tasks.

6.3 Data and Safety Monitoring

A. Data/Safety Monitoring Plan

N/A

B. Data/Safety Monitoring Board Details

Data will be stored on a password protected document and stored on the Rutgers approved Office Cloud - OneDrive. Only the research team will have access to this information. All members of the research team are CITI-trained.

6.4 Reporting Results

A. Individual Subjects’ Results

If patients wish to be notified of the findings of this study, information will be disseminated through a mailing to their preferred address.

B. Aggregate Results

If patients wish to be notified of the findings of this study, information will be disseminated through a mailing to their preferred address.

C. Professional Reporting

The findings of this study are intended to be presented both at professional meeting of health care specialists, as well as be published as a scientific manuscript.

D. Clinical Trials Registration, Results Reporting and Consent Posting

N/A

